Study Title: The Stimulation To Induce Mothers (STIM) Study: A Parallel Group Randomized Controlled Trial

NCT Number: NCT05079841

Unique Protocol Id: 2000031338

Date: 8/11/25

Study Protocol

CLINICAL STUDY PROTOCOL

The Stimulation Therapy to Induce Mothers (STIM) Study: A Multicenter Parallel Group Randomized Controlled Trial

Study Principal Investigator

[name]

Yale University Principal Investigator

[name]

Northwestern University Principal Investigator

[name]

Weill Cornell Medicine Principal Investigator

[name]

Protocol Version

28 July 2025

Version 14

Synopsis

Primary Objective

To determine whether intrapartum nipple stimulation therapy with or without synthetic oxytocin changes the likelihood of achieving a spontaneous vaginal delivery compared to receipt of synthetic oxytocin infusion without nipple stimulation to induce labor.

Secondary Objectives (if applicable)

The secondary objectives are as follows:

1. To determine if women who perform intrapartum nipple stimulation to induce labor have differences in other obstetric and maternal outcomes such as operative vaginal delivery, cesarean delivery, labor duration, postpartum hemorrhage, infection, and morbidities such as higher-order perineal lacerations, ICU admission, or death.
2. To determine if women who perform intrapartum nipple stimulation report differences in pain scores during labor, labor agency and satisfaction scores, postpartum depression scores, and breastfeeding success compared to women who receive only intrapartum exogenous oxytocin infusion.
3. To determine if women who perform intrapartum nipple stimulation to induce labor have similar fetal and neonatal outcomes compared to women who receive only intrapartum exogenous oxytocin infusion.
4. At Yale, to measure circulating plasma and urine concentrations of proteins, microRNA, and small molecules using unbiased “omics” approaches, comparing patients undergoing induction of labor via intrapartum nipple stimulation versus continuous exogenous oxytocin infusion, un-ripened/unlabored control patients, and patients in spontaneous labor.
5. To measure milk maturation biomarkers and milk composition, comparing patients undergoing induction of labor via intrapartum nipple stimulation versus continuous exogenous oxytocin infusion.

Study Design

This is a multi-site, pragmatic, open label parallel group randomized clinical trial of pregnant women at 36 weeks of gestation and greater to compare the effectiveness of inpatient nipple stimulation therapy with or without adjunctive synthetic oxytocin (intervention) versus immediate synthetic oxytocin infusion without nipple stimulation (comparator) during labor induction at Yale New Haven Hospital, Weill Cornell Medicine and Northwestern Memorial Hospital.

Study Population

Nulliparous women with live singleton gestations of 36 weeks and greater and are planned to receive synthetic oxytocin infusion for induction of labor.
Number of Participants A total of 988 participants will be enrolled across all study sites with roughly even distribution.
Number of Study Sites The trial will be conducted at 3 sites: Yale New Haven Hospital (York Street Campus), Weill Cornell Medicine and Northwestern Memorial Hospital.
Primary Outcome Variables The primary outcome is spontaneous vaginal delivery.
Secondary and Exploratory Outcome Variables (if applicable) 
The following secondary maternal outcome variables will be explored: operative vaginal delivery, cesarean delivery, time interval from randomization to delivery, postpartum hemorrhage, infection, 3rd or 4th degree perineal lacerations, maternal death, maternal intensive care unit admission.
 
The following secondary patient-centered outcome variables will be explored: labor pain, feelings of control during labor, satisfaction with the birthing process, ability to express and/or collect colostrum and/or breastmilk intrapartum, depression score, and breastfeeding success.
 
The following secondary perinatal outcome variables will be explored: perinatal death, Apgar score <3 at 5 minutes of life, umbilical artery acidemia, neonatal intensive care unit admission, and a composite neonatal severe morbidity measure. In addition, breastfeeding as the sole source of nutrition (BSSN) at the time of delivery hospitalization within the first 72 hours and maximal percent newborn weight loss up to 14 days post-birth will be examined.
 
In the Yale biospecimen sub-cohort, we will measure circulating plasma concentrations of proteins and microRNA and urine metabolites of prostaglandins using unbiased “omics” approaches, comparing patients undergoing induction of labor via intrapartum nipple stimulation versus continuous exogenous oxytocin infusion. The change in these labor biomarkers will also be evaluated in a cohort of patients presenting in early spontaneous labor who will be evaluated as a control.
 
In the milk biospecimen sub-cohort, we will measure milk conductivity and sodium levels to estimate milk maturation (MM) before and after birth. When milk volume allows, we will also measure milk composition (macronutrients) and will use an unbiased approach to study mammary gland function using milk RNA sequencing. We will compare patients

undergoing induction of labor via intrapartum nipple stimulation versus continuous exogenous oxytocin infusion.

Visit Schedule Table (Optional)
--

Study Flow Chart (optional)

Table of Contents

Synopsis	2
Primary Objective	2
Secondary Objectives (if applicable)	2
Study Duration	2
Study Design	2
Study Population	3
Number of Participants	3
Number of Study Sites	3
Primary Outcome Variables	3
Secondary and Exploratory Outcome Variables (if applicable)	3
Visit Schedule Table (Optional)	4
Study Flow Chart (optional)	4
1 – Introduction	8

1.1 Introductory Statement

This protocol describes the background, design and organization of the trial. It will be reviewed and approved by the Data Safety and Monitoring Board and the Institutional Review Board (IRB) prior to trial initiation. Any changes to the protocol during the study will require approval by the IRB.

2 – Background

2.1 Background/prevalence of research topic

More than one-quarter of the almost four million U.S. women who give birth annually undergo labor induction (1). Generally, labor induction is indicated when the benefits of expeditious delivery outweigh the risks of continuing pregnancy. Additionally, labor induction is increasingly seen as a potentially therapeutic intervention even in the absence of any pregnancy complications for nulliparous women after 39 weeks of gestation (2) (3). However, compared to physiologic labor, induction is often associated with a longer latent phase which can have untoward consequences, including the need for cesarean delivery when an induction attempt fails. (4) Further, it has been shown that women who are induced are less likely to be satisfied with their birth experience compared to those with physiologic labor. (5) Women are increasingly interested in a less medicalized birth experience and desire more control during labor. (6) It has also been suggested that women who are induced or receive exogenous oxytocin may have less optimal breastfeeding outcomes. (7)

Nipple stimulation therapy has been purported as a natural and inexpensive non-medical method for inducing labor. Nipple stimulation was historically used for medically inducing contractions for the purpose of contraction stress testing (CST) (8) (9) (10). But, it is also a biologically plausible method of labor induction that may be more physiologic and allow labor induction to be more efficient and have other benefits. These may include effects related to improved uterine contractility (e.g., decreased postpartum hemorrhage risk), improved patient satisfaction, and stimulation of endogenous oxytocin which may improve breastfeeding and positive emotional responses.

Most prior studies have tested nipple stimulation as a tool to induce physiologic labor at home or did not have an appropriate comparison group. (11) (12) Data on nipple stimulation versus exogenous synthetic oxytocin infusion (the appropriate clinical alternative) are much more limited, but promising. In the two studies (13) (14) analyzed together in a Cochrane review (11), there was a nonsignificant trend towards reduction in cesarean delivery with nipple stimulation ($n=99$, RR 0.60, 95% CI 0.31-1.18), no cases of hyperstimulation, and no significant difference in the number of women with an unfavorable or unchanged cervix. Chayen et al. (13) detected a significantly shorter time to onset of contractions and achievement of 200 Montevideo units without differences in rates of failed induction, tetanic contractions, or fetal bradycardia. Unfortunately, interpretation of the existing data is critically limited by small sample sizes.

Oxytocin is a nine amino acid neuropeptide primarily made in the hypothalamus, and to a lesser extent by other tissues including the endometrium, decidua, amnion, and placenta

(17). Within the nervous system, oxytocin signaling interacts with other neurotransmitter pathways including serotonin and endogenous opioids; surges in oxytocin during parturition have been associated with aspects of maternal adaptation including stress reactivity, mood, and lactation (18). Whether exogenous oxytocin, which theoretically does not cross the blood-brain barrier, interacts with these pathways while stimulating uterine contractions is unknown. Given these unknowns and their potential long-term effects on both maternal and fetal wellbeing, some have argued that exogenous oxytocin use should be used judiciously until more research can be performed on the long-term outcomes associated with exogenous oxytocin (18). These questions suggest that stimulation of endogenous oxytocin may be preferable for some women if it is also effective for labor induction and vaginal birth.

Although oxytocin is one of the most used medications in obstetrics, the kinetics of oxytocin during spontaneous labor and the dosages used for labor induction are based on a few small older trials, and still poorly understood. In an early series evaluating oxytocin signaling during spontaneous labor, among laboring women, plasma oxytocin concentrations were 27.6 pg/mL prior to labor and rose to 45.2 pg/mL in “advanced labor” (19). Among women in spontaneous labor, oxytocin concentration demonstrated minimal change over the course of labor from a mean of 47.2 pg/mL in early labor (less than 4cm dilated) to 45.8 pg/mL when the woman was found to be 10 cm dilation.(20) In contrast, oxytocin concentrations seem to rise in a dose-dependent manner in women being induced with exogenous oxytocin, with a mean plasma concentrations of 110 pg/mL in those receiving infusion at a rate of 10-16 mU/min. (20) (21) (22) It has been shown that over the course of labor, there is decreased responsiveness to oxytocin infusion which may be due to down-regulation of oxytocin receptors ¹⁷⁻²⁰. This phenomenon may contribute to the longer labor durations and labor dystocia patterns seen in induced labor when compared to physiologic labor. Interestingly, in women undergoing breast stimulation for CST, oxytocin concentration initially doubled from baseline after initiation of breast stimulation but then rapidly plateaued ²¹. This study was limited in that it only evaluated oxytocin concentration over 40 minutes and labor was not reported. However, it is plausible that the kinetics of oxytocin concentrations among women who undergo nipple stimulation may be more similar to those experiencing physiologic labor rather than those who are induced with exogenous oxytocin. Lastly, physiologic stimuli, such as parturition or suckling, result in pulsatile release of oxytocin hormone into the peripheral circulation. On the other hand, exogenous synthetic oxytocin is usually administered as a continuous infusion. Previous trials have compared pulsatile versus continuous administration of exogenous oxytocin, and found that less total exogenous oxytocin was required with pulsatile administration, which suggests that it may have behaved as if it was more physiologic.(23) (24) (25) However, pulsatile administration of exogenous oxytocin did not improve clinical outcomes compared to continuous infusion, and it is plausible that even pulsatile administration is not enough to adequately emulate endogenous oxytocin.

In conclusion, despite excellent theoretical acceptance of nipple stimulation for labor induction from patients and providers (26), we lack robust data demonstrating its efficacy and safety. A well-designed randomized clinical trial is needed, particularly in comparison to the standardly accepted clinical alternative (exogenous oxytocin). Further, more data related to oxytocin concentrations and dose response are needed to inform our understanding of the biology of oxytocin during labor induction, especially when comparing exogenous oxytocin versus stimulation of endogenous oxytocin.

It is thought that breast stimulation induces uterine contractility by increasing the level of endogenous oxytocin hormone (15) (16). However, the exact mechanism remains unclear.

To our knowledge, only one previous published randomized clinical trial tested breast stimulation by electric breast pump (Medela, Inc) (13) which showed that the time to reach the active phase of labor was significantly reduced among women who underwent nipple stimulation compared to those who received oxytocin in the hospital setting. There was no difference in the length of labor between groups once women were in the active phase of labor or mode of delivery, but the trial included just 62 women. Reassuringly, only one of the 30 women assigned to breast stimulation requested discontinuation due to nipple soreness after 5.5 hours of intermittent stimulation. There were no serious maternal or perinatal adverse events reported in the trial.

At Yale, our research team recently completed our external pilot feasibility and acceptability randomized clinical trial (Yale IRB #2000029909, Clinicaltrials.gov NCT04756089). In this pilot trial, 24 women were randomized in a 3:1 ratio to nipple stimulation with a breast pump or exogenous oxytocin infusion. Of the 18 women randomized to breast pump stimulation, one woman withdrew due to delay of clinical care and received oxytocin (cross-over rate of 1/24 (4.2%)). Of the 6 women randomized to exogenous oxytocin infusion, one woman did not receive it due to spontaneous labor progress. All other participants followed their assigned intervention (22/24, 92%). The 17 women who performed breast pump stimulation stimulated for a median duration of 198 (IQR 125-291) minutes. There were no serious adverse events for either the mothers or their fetuses/infants.

As part of the pilot feasibility study, our team measured oxytocin in patients performing nipple stimulation and receiving IV oxytocin. We found that patients receiving nipple stimulation achieved regular contractions despite a smaller change in plasma oxytocin compared to patients receiving IV oxytocin to achieve the same contraction pattern. This suggests that nipple stimulation may be activating additional pathways in addition release of endogenous oxytocin.

3 – Rationale/Significance

3.1 Problem Statement

Over 1 million women have their labor induced in the United States each year, and synthetic oxytocin infusion is the most common method used. However, compared to spontaneous labor, medical induction is resource-intensive, has increased obstetric risks, and is associated with less successful breastfeeding. In contrast to endogenous oxytocin hormone which is released in a pulsatile fashion in the brain, synthetic oxytocin is continuously infused intravenously, resulting in important limitations related to efficacy, safety, and cost.

3.2 Purpose of Study/Potential Impact

It has been purported that nipple stimulation may help induce labor and has been successfully utilized for inducing contractions for the purposes of contraction stress testing. It may be an attractive option for induction of labor for both de-medicalization of birth, patient satisfaction, cost reduction, and other clinical benefits. The purpose of this clinical trial is to determine whether nipple stimulation can increase the likelihood of a spontaneous vaginal delivery, and therefore decrease the likelihood of an operative vaginal or cesarean delivery. We also seek to examine whether intrapartum nipple stimulation can decrease labor duration and improve other patient-centered outcomes such as patient pain score, patient agency, patient satisfaction, depression scores, and breastfeeding success. Further, we aim to examine whether breast stimulation is associated with any significant differences in fetal or neonatal outcomes.

We propose a multicenter randomized trial at Yale, Weill Cornell Medicine and Northwestern Universities to compare inpatient nipple stimulation therapy via electric breast pump versus immediate synthetic oxytocin infusion without nipple stimulation for nulliparous women undergoing labor induction. This trial of 988 nulliparous women will provide adequate statistical significance to detect clinically meaningful differences in delivery mode and breastmilk as the sole source of nutrition for newborns. Successful completion of this proposal will provide rigorous data to help us show how this novel and potentially cost-effective method can radically change the way we induce labor and positively impact breastfeeding success and early infant nutrition through lactation.

At Yale, we will additionally measure oxytocin concentration among those who are being induced with nipple stimulation versus exogenous oxytocin, which has not been measured or reported by our groups to our knowledge. In our preliminary findings in 20 patients (n=10 per arm), we found no significant rise in oxytocin among patients who performed nipple stimulation therapy despite achieving adequate contractions, suggesting that other pathways are activated to promote contractions in these patients. Importantly, the biological measurements taken in this study will be correlated with clinical outcomes, which will further inform our understanding of the biology of oxytocin during induction of labor. If regular contractions are achieved with nipple stimulation, comparison between oxytocin levels in the

two groups will help us to understand whether absolute oxytocin concentration is predictive of ultimate mode of delivery. For example, if in more patients, consistent with preliminary findings, breast stimulation is found to result in equal rates of vaginal birth but lower concentration of oxytocin, this would provide evidence that endogenous oxytocin signaling acts through other methods such as affecting oxytocin receptor availability or interaction with other hormones. On the other hand, if oxytocin concentrations are similar or greater in women undergoing breast stimulation, it would suggest that oxytocin concentration is the main driver in successful versus unsuccessful inductions of labor. Similarly, if breast stimulation is found to result in lower oxytocin concentrations and not to be as effective as exogenous oxytocin, this would provide evidence that concentrations do need to reach some critical threshold to effect myometrial contractility.

Because, in our preliminary studies, we have found less rise in maternal oxytocin among patients undergoing nipple stimulation, it is possible that other pathways are being activated in these patients. We intend to explore those other pathways using “omics” approaches to look at plasma proteins and microRNAs and urine prostaglandin metabolites. These studies have the potential to identify the mechanism(s) by which nipple stimulation induces labor, may point to differences with IV oxytocin that lead to the increased morbidities associated with prolonged and failed induction of labor, and may elucidate novel pathways involved in the stimulation of labor, which would contribute to our understanding of induction of labor. In order to understand the mechanisms by which nipple stimulation therapy induces labor, we will also compare the measurements of these biological variables in subjects prior to induction of labor and in control patients in early spontaneous labor.

Lastly, lactation is activated and triggered when a very tightly regulated cascade of events occurs at the end of the pregnancy and during labor, but may be negatively impacted by obstetric interventions. Secretory activation of the mammary gland initiates mature milk production in epithelial cells (usually occur 48-72h postpartum) and then milk ejection is triggered by oxytocin hormone and nipple stimulation (e.g., infant suckling or breast pump). Factors such as nulliparity, labor induction, and cesarean delivery have been shown to increase the risk of early lactation difficulties. Delayed secretory activation is a key predictor of suboptimal breastfeeding outcomes. It is biologically plausible that with IV oxytocin the normal secretory activation process for lactation is altered. Using milk biomarkers, we will examine the effect of nipple stimulation induced labor on lactation initiation in the first 48-72 hours after birth.

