5.1 General Design Description

The proposed study is a multicenter, pragmatic, open label, parallel group randomized trial of nulliparas to compare the effectiveness of intrapartum nipple stimulation therapy with or without adjunctive synthetic oxytocin (intervention) versus immediate synthetic oxytocin

infusion without nipple stimulation (comparator) during labor induction. Potential subjects will be recruited from the Labor & Birth units at three study sites: Yale New Haven Hospital in New Haven, Connecticut, Weill Cornell Medicine in New York, New York and Northwestern Memorial Hospital in Chicago, Illinois. We aim to test the central hypothesis that intrapartum nipple stimulation increases spontaneous vaginal delivery, shortens labor duration, improves other patient-centered outcomes, improves breastfeeding success, and does not increase adverse neonatal and maternal outcomes. We chose a randomized controlled trial, the 'gold standard' of clinical research design, with the goal of obtaining the highest quality evidence to inform clinical practice. Randomly allocating subjects to different interventions minimizes selection bias and results in groups that are comparable with regards to important confounding variables, both measured and unmeasured. Blinding of subjects, maternity care providers, and investigators is not feasible given the intervention being studied (nipple stimulation). With the limitations of the existing data, we estimated our sample size and plan our data analysis based on two-tailed tests. This will ensure that we identify the optimal management strategy for labor induction that increases spontaneous vaginal delivery, irrespective of the direction of our findings.

We will follow the Consolidated Standards of Reporting Trials (CONSORT) guidelines wherever appropriate in the conduct and reporting of this trial. (27) We will use computer-generated random sequences to assign participants to the two interventions with stratification by study site and membrane status (intact versus ruptured). Labor management will be similar in the two groups except for use of nipple stimulation (intervention group) versus immediate synthetic oxytocin infusion without nipple stimulation (control). Analysis will follow the intention-to-treat principle.

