6.1.3 Concomitant therapy

There are no restrictions on use of concomitant medications. However, for those who are randomized to nipple stimulation, the use of exogenous oxytocin intravenous solution will not be permitted until at least two hours of nipple stimulation alone has been attempted, unless this is decided by the treating obstetric provider. Stimulation may be discontinued at any time that the treating obstetric provider decides. If there are any signs of fetal heart rate abnormalities on the cardiotocography, the obstetric provider should provide usual care measures such as discontinuation of stimulation, lateral positioning, intravenous hydration, etc. Initiation of exogenous oxytocin intravenous solution prior to two hours of nipple stimulation alone will be considered a cross-over.

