Specimen collection will be conducted as described in the previously published methodology (38).

For patients in non-spontaneous labor, blood and urine will be collected at 1) prior to cervical ripening, 2) after cervical ripening, and 3) after 2 hours of treatment (IV oxytocin or nipple stimulation). This is a maximum of 3 blood samples per subject. For control patients in spontaneous labor, a blood and urine specimen will be obtained at enrollment. Blood may be drawn in several ways depending on what is clinically appropriate: (1) venipuncture; (2) IV catheter placed as part of standard of care (SOC); and/or (3) IV catheter placed for research purposes. The research IV may be placed in addition to the SOC IV and may be used instead of research venipuncture. That is, research venipuncture and research IV will not both occur at the same time (only one or the other).

Urine samples (amount variable by patient) will be collected mid-stream in a sterile screw-top container 1) prior to cervical ripening, 2) after cervical ripening, and 3) after 2 hours of treatment (IV oxytocin or nipple stimulation). If a patient has an indwelling foley catheter, urine from the tubing will be collected at the time of adequate contractions. If a patient is being intermittently catheterized for urine, a urine sample will be collected as able, but the patient will not undergo additional bladder catheterization for the purpose of this study.

Blood and urine samples may not be collected at one or more of the specified time points due to logistical issues (eg. patient enrolled after cervical ripening, labor floor acuity prevents nurse from drawing blood, patient delivers before time point, etc.) and/or clinical care taking precedence.

Proteomic profiling will be conducted by mass spectrometry at the Keck MS & Proteomics Resource. Prostaglandin measurements will be performed by an external core facility with expertise in prostaglandin mass spectrometry methods (Vanderbilt Eicosanoid Facility). microRNA profiling will be conducted via bulk RNA sequencing by the Yale Center for Genome Analysis/Keck Core.

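### Section 3.2 reads mechanism from an early oxytocin level and a later birth outcome, so it cannot separate the effect of stimulation from that of later synthetic oxytocin

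*Protocol*

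**What the plan says.** Section 3.2 of the protocol explains how the Yale oxytocin measurements will be used. They are to be correlated with clinical outcomes. The comparison opens with a condition: "If regular contractions are achieved with nipple stimulation, comparison between oxytocin levels in the" two groups is said to help show whether oxytocin concentration predicts final mode of delivery. Two readings matter here.

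- If "breast stimulation is found to result in equal rates of vaginal birth but lower concentration of oxytocin", the protocol would take this as evidence that endogenous oxytocin works by other means.
- If stimulation gives "lower oxytocin concentrations and not to be as effective as exogenous oxytocin", then "this would provide evidence that concentrations do need to reach some critical threshold to effect myometrial contractility".

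On treatment, the Synopsis defines the intervention as "inpatient nipple stimulation therapy with or without adjunctive synthetic oxytocin (intervention"), and Section 5.1 repeats this. Under Section 6.1.3, synthetic oxytocin in the stimulation arm "will not be permitted until at least two hours of nipple stimulation alone has been attempted", unless the treating provider decides otherwise. Under Section 6.3, stimulation time does not count towards a failed induction. Section 6.4.1 analyses participants as randomised, whatever they received.

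On sampling, Section 6.3 schedules the on-treatment blood draw "after 2 hours of treatment (IV oxytocin or nipple stimulation"), with at most three blood samples per participant. Sections 6.4.2 and 6.4.3.2 define the primary biomarker comparison as baseline to 2 hours. Sections 4.1 and 6.2.3, and the fold-change wording in Section 6.4.3.2, instead place the oxytocin comparison at first regular or adequate contractions.

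**The concern.** The two halves of each inference are observed at different times and under different treatment. At 2 hours, a stimulation-arm woman managed under Section 6.1.3 has generally had no synthetic oxytocin, while the comparator has had it infused. By the time of birth she may have had an infusion as well. Equal birth with a lower early level is what another pathway would produce. It is also what would be seen if stimulation did nothing and the later infusion led to the birth.

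The threshold sentence has the same weakness in the other direction: later infusion can hide poorer effectiveness of stimulation, so that pattern might not appear even if it were true of stimulation alone. What is at stake is the mechanistic conclusion of the oxytocin work. The primary trial result is not affected.

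**Working it through.** **Inputs**
- Oxytocin difference 24.25%, SD 40.8, 45 per group, detectable difference 23.6% at 48 per group: Section 6.4.2, biomarker table. The table notes trace the difference to the investigators' preliminary data, with the effect size taken at adequate contractions.
- Two-sided alpha 0.05, 80% power, 48 per exposure group: Section 6.4.2.
- 192 main-trial participants in the Yale sub-study: Section 5.3.1. That is 96 per arm if split 1:1 (my assumption).
- Spontaneous vaginal delivery 64% in the comparator: Section 6.4.2. It stands in here for the vaginal birth rate.
- One of 18 pilot pump-arm women received oxytocin, 1/18 = 5.6%: Section 2.1.

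**Step 1, the plan's own figure.** n per group = 2 × (1.960 + 0.842)² × (40.8/24.25)² = 2 × 7.85 × 2.83 = 44.4, so 45. The t-test version gives 45.4, and the detectable difference at 48 per group is 23.6%. Both stated figures reproduce.

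**Step 2, oxytocin half.** The standardised difference is 24.25/40.8 = 0.594. The t-test probability of significantly lower oxytocin is 0.822 at 48 per arm and 0.984 at 96. If a share c of the stimulation arm is already infused at the sample and has the comparator's mean level, the difference becomes (1 − c) × 24.25.

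**Step 3, birth half.** Suppose stimulation is inert, later infusion makes the true rates equal at 64%, and equal means p>0.05. The exact binomial probability of a non-significant chi-square test is 0.95 at 48, 96 or 494 per arm.

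**Step 4, both halves,** multiplied as if independent and ignoring Section 3.2's contraction condition:

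| Share infused at sample | Lower oxytocin, n=48 | Both, n=48 | Lower oxytocin, n=96 | Both, n=96 |
|---|---|---|---|---|
| 0% (2-hour sample) | 0.822 | 0.78 | 0.984 | 0.93 |
| 5.6% (2-hour sample, pilot early cross-over) | 0.777 | 0.74 | 0.972 | 0.92 |
| 25% (sample at adequate contractions) | 0.580 | 0.55 | 0.867 | 0.82 |
| 50% (same) | 0.302 | 0.29 | 0.535 | 0.51 |
| 75% (same) | 0.108 | 0.10 | 0.175 | 0.17 |
| 100% (same) | 0.025 | 0.02 | 0.025 | 0.02 |

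**Step 5, sensitivity.** If inert stimulation also cost 5 points in delivery (59% versus 64%), a non-significant result has probability 0.922 at 48 per arm and 0.635 at 494 per arm. With the 2-hour sample and the full-trial birth comparison, the joint probability is then 0.822 × 0.635 = 0.52 (48 sampled per arm) or 0.984 × 0.635 = 0.62 (96 per arm).

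**The case against.** Section 3.2 is rationale. It introduces the example as an example and says only that such a result would provide evidence. Section 6.4.3.2 plans no analysis that pairs birth with oxytocin; the one labor outcome modelled with biomarkers is time to active labor, and that is exploratory. This stands.

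The example is also conditioned on regular contractions under stimulation, so inert stimulation that produces no contractions falls outside it. This stands in part. No analysis set applies the condition, and women who have been ripened or have ruptured membranes may contract without any effect of stimulation. Section 2.1 cites a mean of 47.2 pg/mL in early spontaneous labor against 110 pg/mL on infusion at 10-16 mU/min, so contractions with lower oxytocin need not mean that stimulation worked.

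Sections 4.1 and 6.2.3 time the oxytocin comparison at contractions, where the joint probability can be small. That is correct, but Section 6.3 schedules no blood draw then. If one were taken, infused stimulation-arm women could show similar oxytocin, which Section 3.2 reads as concentration being the main driver. Later infusion still enters the inference.

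Finally, parts of a remedy exist. Section 5.2.2 separates women who cross over to infusion for urine prostaglandins, and Section 6.4.3.1 plans a sensitivity analysis by method received. The data collection form is an appendix that is not shown, so infusion start time and dose may already be recorded. None of this is tied to the inference in Section 3.2.

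**Conclusion.** The point holds as a limit on interpretation. With oxytocin sampled at 2 hours and birth possibly following later infusion, neither the other-pathway sentence nor the threshold sentence separates stimulation from infusion.

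A reader might go further and infer that the protocol fixes a decision rule which an inert intervention would usually pass, so that the sub-study would report a mechanism for something that did nothing. The documents do not support that. There is no formal rule, and the text carries a contraction condition. The 0.78 to 0.93 range belongs to the 2-hour sample only. It uses preliminary-data inputs that are not 2-hour results under inert stimulation, reads equal as p>0.05, treats the two halves as independent, and assumes that later infusion fully restores the birth rate. The protocol gives no figure for how many stimulation-arm women will be infused. Under the other stated time point the range is 0.02 to 0.82, depending on that share (25% to 100% infused).

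The change is still worth making, because Section 3.2 states the conclusion to be drawn and commits to correlating these measurements with outcomes.

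**What to change.** 1. Reconcile the oxytocin sampling time: Section 6.3, Section 6.4.2 and the primary comparison in Section 6.4.3.2 (2 hours) against Sections 4.1 and 6.2.3 and the fold-change wording in Section 6.4.3.2 (first regular or adequate contractions).
2. In Section 3.2 and the sub-study analysis, base the mechanistic inference on a response reached before any synthetic oxytocin, such as adequate contractions or active labor. Count all randomised sub-study women, and treat those infused first as non-responders.
3. Use synthetic-oxytocin start time and cumulative dose in both arms, abstracting them from the record if they are not already collected.
4. State that equal vaginal birth with lower early oxytocin is not by itself evidence of another pathway when stimulation-arm women later received infusion, and put the same limit on the threshold sentence.

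The cost is protocol and analysis wording and at most two abstracted variables. Treatment, sample size and the primary analysis are unchanged. The downside is a narrower mechanistic claim.
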